The purpose of this Statistical Analysis Plan (SAP) is to provide a detailed statement of the intended statistical analyses to be performed on data collected in the DDX-BRO study. The SAP is intended to be a document that stands alone from the study protocol to which it will adhere in the main points of analysis. However, the SAP can undergo revision outside of the protocol. It is not anticipated that revisions of the SAP that are in the spirit of the pre-specified protocol analysis would require review by an ethics committee. The analysis plan also outlines the proposed layout of tables and figures to be presented in the main results paper.

6 Study Objectives and Endpoints

6.1 Study Objectives

The overall objective of this research project is to reveal the intended and unintended micro-, meso- and macro-level consequences by providing a differential diagnoses (DDx) generator (computerized diagnostic decision support system; CDDS) to physicians in an ED.

The primary (micro-level) objective is to assess the effect of the DDx generator usage on diagnostic quality in patients admitted to the ED. Our primary hypothesis is that ED patients will have a slightly but significant reduced diagnostic quality risk when physicians are asked to consult the provided DDx generator after the first physical examination.

Secondary objectives are

- on the micro-level, to investigate how the use of a DDx generator affects patient related outcomes such as mortality, length of stay, or unscheduled revisits.
- on the meso-level, to understand how DDx generator affect diagnostic workflow in the ED and physicians' advice seeking, collaboration and confidence calibration.
- on the macro-level, to investigate the economic implications of DDx generators utilization in ED and to evaluate the educational implications for physician training.

The safety objective corresponds to the primary outcome, namely how the use of a DDx generator affects diagnostic safety in patients admitted to the ED.

6.2 Endpoints

6.2.1 Primary endpoint

The primary endpoint is a binary score indicating the risk of reduced diagnostic quality, composed of:

- death within 14d days after ED discharge (yes/no)
- unscheduled medical care (ED revisits, general practitioner (GP) visits or hospitalization) within 14 days after ED discharge (yes/no)
- unexpected intensive care unit admission from ward within 24h when hospitalized (yes/no)
- diagnostic discrepancy between the ED discharge diagnosis and the current diagnosis 14 days after ED admission (yes/no)

The primary endpoint is *true* (1), if one or multiple of the criteria above become true, and *false* (0) if none of the criteria above occur.

Secondary endpoints include

- all variables of the primary endpoint individually
- unscheduled ED/GP revisits after 72h and 7 days
- length of ED stay
- length of hospital stay if hospitalized
- diagnostic tests in ED
- diagnostic tests after ED
- resource consumption in ED (costs)
- care consumption after ED discharge
- discharge destination
- number and patterns of DDx provided by the physicians
- number of cases where the generated DDx list entails the diagnoses after 14d
- diagnostic error based on full chart review for a random subset
- CDDS usage (timing and number of queries)

Safety endpoints correspond to the endpoint specified in the primary endpoint (except diagnostic discrepancy). Additionally, rates of serious adverse events will be assessed.

Additional outcomes are physician confidence calibration, advice seeking and collaboration assessed by qualitative methods (physician observations, interviews and focus groups) to understand how DDx generator affect diagnostic workflow in the ED and physicians' advice seeking, collaboration and confidence calibration. These outcomes focus namely on physicians and their diagnostic process as a quality assurance. Specification of study endpoints are in chapter 7.5 Study variables.

7 Study Methods

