7.5 Study variables

7.5.1 Primary endpoint

Variables	Description	Scale	Time Window*
Diagnostic quality risk	The score is positive and patients at risk for a diagnostic error if one or multiple of the criteria below becomes true:	0, not at risk 1, at risk	14±4 days
Death	Patient died during time of follow-up	0, no 1, yes	14±4 days
Unscheduled medical care	Patient had at least one medical appointment (GP, ED, Hospital, rehabilitation or others) after ED or hospital discharge that was related to the initial ED presentation but not scheduled at the time of ED or hospital discharge. The criteria is fulfilled if the medical appointment was registered in the hospitals' EHR or reported by the patient or GP during follow-up.	0, no 1, yes	14±4 days
Unexpected Intensive Care Unit admission	Patient was first admitted to the ward and then transferred to the intensive care unit (or next upscale in care) within 24 hours.	0, no 1, yes	up to 24 hours after ED discharge
Diagnostic discrepancy between ED diagnosis and diagnosis at follow-up	The primary diagnosis has changed during the time of follow-up and is medically different compared to the primary ED diagnosis. The criterion is not fulfilled if the diagnosis at follow-up is verbatim or medical identical with the primary ED discharge diagnosis, just more precise or a complication, i.e. diagnosis at follow-up was not foreseeable at the time of ED diagnosis. The classification follows a pre-defined scheme as used in a previous study (2). The diagnosis at 14d is based on the documentation of the GP or treating Hospital at the time of follow-up. If patients did not report any medical care after ED, we assume that the diagnosis did not change since ED or hospital discharge.	0, no 1, yes	14±4 days

*Follow-up was performed within 14±4 days. All events between baseline and follow-up were documented including time of event (e.g. death date or date of re-visits)

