10.3 Protocol Deviations

Protocol deviations are considered major if the CDDS were not used during interventional periods or used during control periods. This protocol deviations are addressed by the PP-analysis and sub-analysis described in section **Fehler! Verweisquelle konnte nicht gefunden werden.** and **Fehler! Verweisquelle konnte nicht gefunden werden.** Follow-up phone interviews may have been conducted after 14±4 days because some patients returned the call after the timeframe or specifically requested a call to on one of the subsequent days. We will perform a primary efficacy sensitivity analysis without these patients if the number of cases exhibits more than 5%. We do not expect any other protocol deviations that may interfere with the primary efficacy analysis.

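### The primary endpoint is defined within 14 days of ED discharge, but its derivation has no date cut, so the follow-up call date sets each patient's event window

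*SAP*

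**What the plan says.** SAP 6.2.1 gives fixed limits. Death counts as "death within 14d days after ED discharge (yes/no"), and the second component is "unscheduled medical care (ED revisits, general practitioner (GP) visits or hospitalization) within 14 days after ED discharge (yes/no"). The diagnostic component is anchored differently: "diagnostic discrepancy between the ED discharge diagnosis and the current diagnosis 14 days after ED admission (yes/no").

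SAP 7.5.1 describes the same components differently. Death becomes "Patient died during time of follow-up". The time window for the composite, death, unscheduled care and discrepancy is 14±4 days. Qualifying care covers "GP, ED, Hospital, rehabilitation or others", where 6.2.1 lists only ED, GP and hospitalization. The footnote adds: "All events between baseline and follow-up were documented including time of event".

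SAP 10.2, which the programmer will follow, has no date condition. [death] is true when the reason for non-completion is death. [revisit_yn] is true when any documented appointment was both unplanned and related, or probably related, to the first visit.

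SAP 10.3 says "Follow-up phone interviews may have been conducted after 14±4 days". It plans a sensitivity analysis "without these patients if the number of cases exhibits more than 5" per cent. Section 11.1 runs the primary analysis on the ITT set, so these patients stay in it.

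**The concern.** A tolerance on when a patient is telephoned is ordinary. Here the call also closes the period over which events are counted, because nothing truncates at day 14. That fails in both directions:

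- A related revisit on day 20, reported in a late call, is positive under 10.2 but outside 6.2.1.
- A death on day 12 in a patient already followed up on day 10 is inside 6.2.1. The 10.2 rule would miss it if that patient is recorded as having completed the study.

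Two programmers working from different sections could therefore build different primary endpoints from the same data. The stake is a clear definition of the outcome. There would also be some distortion of the treatment contrast if call timing differed between conditions.

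**Working it through.** **The plan's own figure.** Section 8 assumes 12% in control, a 5-point difference, 80% power, alpha 0.05 (two-sided per section 11), an ICC from 0.01 and 10% loss. Two proportions, 12% against 7%, need 539 per arm, or 1,078. Multiplying by (1 − 0.01) for the cross-over gives 1,067, and dividing by 0.90 gives 1,186. The SAP states 1,184, so 12% against 7% at day 14 is the planned contrast.

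**Risk by call day, constant hazard (assumption).** h = −ln(0.88)/14 = 0.00913 per day, and risk(d) = 1 − exp(−h·d).

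| Call day | All accrues, constant hazard | Half accrues over time | Front-loaded (Weibull shape 0.5) |
|---|---|---|---|
| 10 | 8.7% | 10.3% | 10.2% |
| 14 | 12.0% | 12.0% | 12.0% |
| 18 | 15.2% | 13.6% | 13.5% |

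The half-accruing column holds 6 of the 12 points fixed and lets the rest accrue at a constant hazard. The front-loaded column is 1 − 0.88^√(d/14). The day 10 to 18 spread is 6.4 points in the first case and about 3.3 in the other two. The first column is near the upper end, because the ICU component has a fixed 24-hour window and does not depend on the call.

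**Timing unrelated to condition.** Spread calls evenly over days 10 to 18 under the constant hazard. Mean risk is 11.98% in control and 6.99% in intervention (h = −ln(0.93)/14 = 0.00518). The difference is 4.98 points against 5 planned. The control variance p(1 − p) is 0.1054 against 0.1056. Power is essentially unchanged.

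This near-cancellation needs calls centred on day 14. At the extremes, the 5-point contrast becomes 3.7 points if every call falls on day 10, and about 6.2 if every call falls on day 18.

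**Timing that differs by condition, with no true effect.** A one-day difference in mean call time (14.5 against 13.5) moves the contrast by:

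- exp(−13.5h) − exp(−14.5h) = 0.80 points under the constant hazard;
- 0.41 points if half the composite accrues over time;
- 0.40 points if events are front-loaded.

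Two days would give about 0.8 to 1.6 points.

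**The case against.** The strongest reply is that 6.2.1 is a summary. It refers the reader to chapter 7.5 for the specification, and 7.5.1 and the schedule in 7.4 both say 14±4 days. Section 9.5 attributes the same window to the protocol for death and unscheduled care as safety outcomes. On that reading, aligning 6.2.1 with 7.5 would be as valid as the reverse. This explains the wording of days 10 to 18. It does not cover events reported in calls after day 18, which fall outside both windows and are still counted.

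A reader might infer that the 6.4-point spread exceeds the 5-point target, and hence that the trial result is biased or under-powered. The documents do not support that. The spread compares two patients, whereas the target compares two conditions. Follow-up nurses are blinded (7.3), sites alternate between conditions (7.1), and the model includes period and site (11.1). Nothing in the SAP shows that call timing differs by condition. What remains is a possibility: condition is set by site and calendar period, so a follow-up backlog at one site in one period would fall wholly in one condition. The model has no call-time or site-by-period term to absorb it.

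Three further points stand against a larger claim:

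- ED stay is recorded as at most 24 hours (7.5.2), so counting from admission or from discharge differs by about a day at most.
- Unscheduled care at 3 and 7 days is already analysed, and both windows close before the earliest in-window call.
- The late-call exclusion in 10.3 only supplements the primary analysis, so removing it would be a matter of preference.

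**Conclusion.** The inconsistency is real and lies in the text. As written, the plan counts events outside its own 14-day definition, can miss events inside it after an early call, and lists two sets of care settings. It should be settled before efficacy analysis, and section 9.1 provides for final SAP changes at that stage.

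The numerical impact is modest unless call timing differs by condition. Individual control risk varies from 8.7% to 15.2% between calls on days 10 and 18, or from about 10.2% to 13.6% under the milder assumptions. Mean risk and power barely move when timing is unrelated to condition and centred on day 14. A difference in mean call time would shift the contrast by about 0.4 to 0.8 points per day. These figures rest on assumed hazard shapes, and the SAP does not say how many late calls there are or how late. Neither bias nor loss of power is shown.

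The 10.3 sensitivity analysis does not repair the definition. It is conditional, ignores variation within days 10 to 18, and removes late responders when their events could simply be truncated.

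**What to change.** - In 10.2, derive [death] and [revisit_yn] from the recorded event dates, counting only events up to day 14 after ED discharge, as in 6.2.1.
- Keep patients with late calls in the primary analysis and ignore their events after that day.
- For calls on days 10 to 13, complete the window from EHR or GP records where available. Otherwise state that follow-up ended early.
- State the reference date for the follow-up diagnosis. The SAP shows no date of diagnosis change, so a date filter alone cannot settle this component.
- Use one list of qualifying care settings in 6.2.1 and 7.5.1.
- Reconcile the 14±4-day wording in 7.5 and 9.5 with 6.2.1, presenting ±4 days as the contact tolerance.

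The exclusion analysis in 10.3 may stay as supplementary.

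Cost: SAP wording, a filter on death and visit dates (visit dates are already needed for the 3- and 7-day endpoints), some record checking for early calls, and slightly fewer counted events. The planned sample size does not change.

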7.1 General Study Design and Plan

DDX-BRO is an open label, cross sectional, multi-center, six-period cross-over cluster-randomized controlled superiority trial. Participating EDs were randomly allocated to two different sequences of alternating intervention and control periods of two months each. During intervention periods, physicians of the respective ED were asked to query the CDDS for DDx. During the control period, the DDx generator will not be provided to the physician and the diagnostic process will follow the usual care. No wash-out periods will be applied as no substantial cross-over effects are expected given the nature of the intervention.

7.2 Inclusion-Exclusion Criteria and General Study Population

Subjects fulfilling all of the following inclusion criteria are eligible for the investigation:

- Informed Consent signed by the subject.
- Presentation to the ED with fever, abdominal pain, syncope or non-specific complaint (NSC) as chief complaint because all these complaints occur frequently, can result from a large number of underlying diseases and thus provide room for diagnostic error. Further, there are no universally agreed algorithms for the diagnostic workup of any of these symptoms (as there is for chest pain, for example). NSC are defined as all chief complaints not included in the check list of specific complaints according to Nemec et al. 2010 (1) or as degraded general condition (german: "reduzierter Allgemeinzustand", "AZ-Reduktion" or similar) as chief complaint.
- Triage as "no acute life-threatening condition" because study intervention would not be feasible in many cases.
- The study subject is 18 years old or older.

The presence of any one of the following exclusion criteria will lead to exclusion of the participant:

- Trauma as chief complaint, because there are standardized diagnostic workups, most trauma patients receive radiographic imaging and the potential benefit of a DDx generator is questionable.
- Pregnancy (anamnestic), because options for diagnostic workup are severely constrained in these patients and presentation is mostly related to pregnancy and its complications, reducing room for error to occur and be remediated.
- Worsening of a known pre-existing condition or medical referral with a definite diagnosis, because the diagnosis is clear in this case
- Inability to follow the informed consent and investigation procedures, e.g. due to language barriers, psychological disorder, admittance via police, detainee status.
- Previous enrolment into the current investigation

7.4 Study Assessments

Investigation Periods	Screening	Consent (ICF)	Treatment, Intervention Period		Follow-up
Emergency care in the emergency room	Admittance and triage	Waiting time	Medical examination and treatment		discharged or hospitalized
Time	-1 to -5h	-1 to -5h	0 to 1h	1h + LOS	14d±4d
A) Enrolment					
In- /Exclusion criteria	x				
Patient information		x			
Patient consent (ICF)		x			
B) Intervention					
CDDS application during intervention period			x	(x)	
CDDS usage monitoring by study nurses			x		
C) Assessments (CR: performed within clinical routine as appropriate)					
Demographics	x				
Chief complaint	CR				
Triage assessment	CR				
Medical history			CR		
Physical examination			CR	CR	
Vital signs			CR	CR	
Laboratory tests			CR	CR	
Other diagnostic tests			CR	CR	
CDDS input / output data collection			x	(x)	
Physician questionnaire			x	(x)	
Patient telephone interviews					x
Medical record review from ED, hospital and/or GP			x	x	x
Serious Adverse Events, Adverse device effects			x	x	x
Device Deficiencies			x	x	
D) Primary Outcome Score					
All-cause mortality					x
Unscheduled medical care if discharged (GP, ED revisit, hospitalization)					x
Unexpected ICU admission or upscale in care within 24h if hospitalized					x
Current diagnosis for presenting complaint				x	x
E) Secondary Outcomes					

Number and cost of ED diagnostic tests				x	x
Time to ED diagnosis				x	
ED differential diagnoses				x	
Physician confidence in ED diagnosis				x	
Discharge destination				CR	
ED LOS				CR	
Hospital LOS if hospitalized					CR
CDDS usage (number of queries)		x	(x)		
Patient reported outcomes					x

ED, Emergency room; ICU, intensive care unit; CDDS, computerized diagnostic decision support system; GP, general practitioner; LOS, length of stay; CR, clinical routine

7.5 Study variables

7.5.1 Primary endpoint

Variables	Description	Scale	Time Window*
Diagnostic quality risk	The score is positive and patients at risk for a diagnostic error if one or multiple of the criteria below becomes true:	0, not at risk 1, at risk	14±4 days
Death	Patient died during time of follow-up	0, no 1, yes	14±4 days
Unscheduled medical care	Patient had at least one medical appointment (GP, ED, Hospital, rehabilitation or others) after ED or hospital discharge that was related to the initial ED presentation but not scheduled at the time of ED or hospital discharge. The criteria is fulfilled if the medical appointment was registered in the hospitals' EHR or reported by the patient or GP during follow-up.	0, no 1, yes	14±4 days
Unexpected Intensive Care Unit admission	Patient was first admitted to the ward and then transferred to the intensive care unit (or next upscale in care) within 24 hours.	0, no 1, yes	up to 24 hours after ED discharge
Diagnostic discrepancy between ED diagnosis and diagnosis at follow-up	The primary diagnosis has changed during the time of follow-up and is medically different compared to the primary ED diagnosis. The criterion is not fulfilled if the diagnosis at follow-up is verbatim or medical identical with the primary ED discharge diagnosis, just more precise or a complication, i.e. diagnosis at follow-up was not foreseeable at the time of ED diagnosis. The classification follows a pre-defined scheme as used in a previous study (2). The diagnosis at 14d is based on the documentation of the GP or treating Hospital at the time of follow-up. If patients did not report any medical care after ED, we assume that the diagnosis did not change since ED or hospital discharge.	0, no 1, yes	14±4 days

*Follow-up was performed within 14±4 days. All events between baseline and follow-up were documented including time of event (e.g. death date or date of re-visits)

7.5.2 Secondary endpoints

Variables	Description	Scale	Time Window*
Death	see primary endpoint above	0, no 1, yes	14±4 days
Unscheduled medical care	see primary endpoint above	0, no 1, yes	14±4 days
Unscheduled medical care	see primary endpoint above	0, no 1, yes	7 days
Unscheduled medical care	see primary endpoint above	0, no 1, yes	3 days
Unexpected Intensive Care Unit admission	see primary endpoint above	0, no 1, yes	24h
Diagnostic discrepancy between ED diagnosis and diagnosis at follow-up	see primary endpoint above	0, no 1, yes	14±4 days
Length of ED stay	Time difference between ED admittance to ED discharge or ward admission	number of hours (ranging from 0 up to 24 hours)	up to 24 hours after ED discharge
Length of hospital stay if hospitalized	Days between ward admission and hospital discharge	number of days ranging from 0 days (discharged at admission day) to 18 days (if hospitalized at end of follow-up)	up to 18 days
Diagnostic tests in ED	Data are sought from the EHR to indicate if the patient received one of the following diagnostic tests during the ED stay: laboratory (blood, urine or sputum), MRI, CT, sonography, x-ray, other. Data is collected for each diagnostic type and corresponding subgroups (e.g abdominal CT, head CT etc.)	0, no 1, yes	length of ED stay, up to 24 hours
ED resource consumption (costs)	Hospitals administrative cost accounting data will be used as a measure of costs that were caused during patient's ED stay. Total costs and subcategories of the cost unit accounting are collected.	numeric in Swiss Francs (CHF)	length of ED stay, up to 24 hours
Total resource consumption (costs)	Hospitals administrative cost accounting data will be used as a measure of costs that were caused during patient's ED and hospital stay if hospitalized. Total costs and subcategories of the cost unit accounting are collected.	numeric in Swiss Francs (CHF)	length of hospital stay, up to 24 hours
Diagnostic tests after ED	Data are sought from the EHR, GP or patient reported during follow-up to indicate if the patient received one of the following diagnostic tests on one of the medical appointments (see care consumption above). laboratory (blood, urine or sputum), MRI, CT, sonography, x-ray, other	0, no 1, yes	14±4 days
Discharge destination	Discharge from ED to one of following locations	0, home 1, hospital (intern) 2, hospital (extern) 3, nursing home 4, rehabilitation 88, other	length of ED stay, up to 24 hours

Number of DDx provided by the physicians	Number of differential diagnoses provided in the ER discharge letter or EHR documentation.	numeric	length of ED stay, up to 24 hours
Number of cases where the generated DDx list entails the primary diagnosis after 14d	The primary diagnosis at end of follow-up was provided at least once of one of the provided DDx-list resulting from a DDx-Generator query.	0, no 1, yes	14±4 days
Diagnostic error based on full chart review for a random subset	For a random subset of 50 patients with and 50 patients without positive primary endpoint, a full chart review will be performed to identify diagnostic errors using the Safer Dx Instrument (3) The Instrument includes 13 statements to the presence of a diagnostic error.	Likert Scale from 1 (strongly disagree) to 7 (strongly agree).	
Tracked CDDS usage	All queries of the DDx-Generator are tracked and recorded in the study database. 
 - Number of queries per patient and physician - Number of queries per patient and physician - Time difference in hours between ED admittance and query 	numeric	length of ED stay, up to 24 hours
Self-reported CDDS usage and impact	Physicians questioned with an online survey regarding the use and impact of the generator in the diagnostic process for the individual patient. The questionnaire includes Nine statements regarding diagnosis, confidence, diagnostics, consultations and general helpfulness.	0, no 1, yes	0-3 days
*Follow-up was performed within 14±4 days. All events between baseline and follow-up were documented including time of event (e.g death date or date of re-visits).			

